Overall: Assessments will be made at Week 0 (Baseline) with follow-up visits every 4 weeks thereafter, for a total of up to 7 study related assessments (Week 0 (Baseline), Weeks 4, 8, 12, 16, 20 and Week 24 (Final Evaluation)). Subjects will return to the clinic for all follow-up assessments.

Baseline: Initial demographics and a brief medical history will be collected at Baseline from subjects or via chart abstraction after informed consent and after meeting all inclusion/exclusion criteria. Data on the primary endpoint will be collected: pressure ulcer size (stage, length, width, and depth) via clinician measurement with photographic documentation. Secondary endpoints of infection status of the ulcer including signs/symptoms of infection, amount and type of exudates, color and type of tissue/character of the wound bed and health care resource utilization (wound-related) and adverse events will also be collected at Baseline. The wound surface area (length x width), amount of exudate and tissue type will be recorded using the PUSH Tool 3.0, and a PUSH baseline score will be calculated (PUSH score).

Follow-up visits: Information collected at each follow up visit will include information on the pressure ulcer size (length, width, depth via clinician measurement with photographic documentation), PUSH sub-scores and total score, time to complete closure of wound, infection status of the ulcer including signs/symptoms of infection, health care resource utilization (wound-related) and adverse events. If applicable, reason for early discontinuation will be recorded. Treatment-related adverse events will be collected at all follow-up visits.

Procedures	Baseline	Follow-Ups	Final Evaluation
Study procedures			
Informed Consent and Privacy Authorization	X		
Inclusion/Exclusion Criteria	X		
Demographics			
Age, Race, Gender, Education, Insurance Status (from chart)	X		
Marital, Employment, Insurance Status			
Medical History			
Height, Weight, Smoking/Tobacco Status	X		
Spinal Cord Injury Information (from chart)	X		
Type of Bladder Management	X		
Number of Concomitant Ulcers	X	X	X
Use of Antibiotics	X	X	X
Primary efficacy endpoint			
Ulcer Depth, Length, Width, Stage	X	X	X
Secondary endpoints			
Wound Infection Status	X	X	X
Amount and Type of Exudate	X	X	X
Color/Type of Tissue/Character of Wound Bed	X	X	X
PUSH Scores	X	X	X
Health Care Resource Utilization (Wound-Related)		X	X
Safety			
Reason for Early Discontinuation (if applicable)		X	
Adverse Events	X	X	X

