
 – Patient has any wound that at enrollment is scheduled for surgical closure within 14 days – Use of any immunosuppressant medications (for example, cyclosporine, methylprednisolone, prednisone, methotrexate, alefacept, or infliximab) within 30 days of screening – Is unable to fully comply with the study requirements; for example, if the wound is in a place that the patient cannot reach him/herself and as such requires a caregiver to apply the study product, if the patient does not have consistent twice daily access to a caregiver, this patient would be ineligible for the study – Any condition or situation which, in the Investigator’s opinion, puts the subject at significant risk, could confound the study results, or may interfere significantly with the subject’s participation in the study – Patient is medically unstable or has a life expectancy of less than 12 months – Patient is pregnant – Patient is a woman of child-bearing potential and does not consent to or receive a screening urine pregnancy test prior to study enrollment – Current enrollment in an investigational drug or device study or participation in such a study within the last 30 days prior to Baseline (Week 0) 	

Name of Sponsor/Company:	Oculus Innovative Sciences, Inc.
Name of Finished Product:	Microcyn [®] Skin and Wound Care with preservatives (“Microcyn”)
Name of Active Ingredient:	N/A
Test Article, Dose, and Mode of Administration:	
Microcyn [®] Skin and Wound Care with preservatives, applied twice daily, topical administration	
Statistical Analyses:	
Efficacy Analyses:	
Efficacy will be tested via T-tests of percent change in wound size using an intention to treat (ITT) approach as well as a per protocol analysis. Secondary analyses will include Kaplan-Meier analysis to estimate time to complete wound closure, and may include linear and logistical regression to estimate the impact of patient characteristics on study endpoints, with special emphasis on variables that affect healing times, such as diabetes and smoking status. The efficacy population will include all patients entered into the study.	
Safety Analyses:	
Safety analyses will be conducted via Fischer’s exact tests, chi-square, and t-tests, as applicable. The safety population will include all subjects exposed to the any study product (Microcyn or saline) who have provided any post-treatment safety information.	
Sample Size Justification:	

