The numbers above represent “nodes” of care with nodes 1-4 representing the four basic components of an effective pressure ulcer care plan: (Node 1) necrotic tissue debridement; (Node 2) initial wound cleansing and repeated cleansing with each dressing change; (Node 3), prevention, diagnose and treatment of infection; and (Node 4), using a wet ulcer dressing that keeps surrounding tissue dry. Nodes 5-14 as shown above represent

assessment and reassessment of the healing strategy and its outcome(s) to ensure optimal healing.

Spinal cord injured patients are an especially vulnerable population for pressure ulcers because of both the immobility rendered by resultant paralysis and of impaired sensation. The National Spinal Cord Injury Statistical Center (NSCISC) estimates that between 231,000 and 311,000 Americans are living with a spinal cord injury (SCI), with approximately 12,000 new cases each year.⁴ As a result of increased research and interest, remarkable progress has been made in improving the quality of life and life expectancy for SCI patients. Secondary complications, however, continue to challenge individuals living with SCI and their caregivers. Pressure ulcers, in particular, “remain the single most important medical complication in terms of loss of time in educational or vocational pursuits, increased hospital stay and resulting financial expenditures.”⁵ In patients with paraplegia, pressure ulcers are the leading cause of rehospitalization;⁶ across injury levels, sepsis from pressure ulcers and genitourinary tract infections are the leading cause of death in Veterans with SCI.⁷

Recent cost estimates on treating pressure ulcers in SCI patients indicate a range of \$2,000 to \$70,000 per wound, with an annual aggregate cost of approximately \$2.2 to \$3.6 billion in the United States alone.⁸ In a retrospective study reviewing medical records of veterans with spinal cord injury, it was found that over 50% of pressure ulcers did not fully heal over the three-year study period, with over 70% of Stage IV ulcers remaining unhealed despite surgeries and multiple hospitalizations.⁹

⁴ *Spinal Cord Injury Facts and Figures at a Glance*, National Spinal Cord Injury Statistical Center, Birmingham, Alabama, February 2010, <https://www.nscisc.uab.edu>.

⁵ Jackson, AB., *Secondary Conditions of Spinal Cord Injury*, Spinal Cord Injury Network, <http://www.spinalcord.uab.edu/show.asp?durki=32106>.

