2.4.2. INCLUSION CRITERIA

All subjects must meet the following inclusion criteria to participate in the study:

1. Written informed consent including authorization to release health information
2. Male or female outpatients age over the age of 18
 - a. If a woman of child bearing potential (WOCBP), not pregnant or nursing, and;
 - b. If WOCBP, must consent to a screening urine pregnancy test and remain on a reliable birth control method for duration of study
3. Spinal cord injured
4. One or more Stage III or Stage IV pressure wound located anywhere on the body.
5. Willing and able to fulfill all obligations of the study, including attending all study visits
6. Has the ability himself or herself, or via reliable and regular access to a caregiver, to apply study product twice daily.

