3.2. SCHEDULE OF VISITS AND PROCEDURES

A schedule of visits and procedures is provided in Table 1.

Table 1: Schedule of Visits and Procedures

Procedures	Baseline	Follow-Ups	Final Evaluation
Study procedures			
Informed Consent and Privacy Authorization	X		
Inclusion/Exclusion Criteria	X		
Demographics			
Age, Race, Gender, Education Insurance Status (from chart)	X		
Marital, Employment, Insurance Status	X		
Medical History			
Height, Weight, Smoking/Tobacco Status	X		
Spinal Cord Injury Information (from chart)	X		
Type of Bladder Management	X		
Number of Concomitant Ulcers	X	X	X
Use of Antibiotics	X	X	X
Primary efficacy endpoint			
Ulcer Depth, Length, Width, Stage	X	X	X
Secondary endpoints			
Wound Infection Status	X	X	X
Amount and Type of Exudate	X	X	X
Color/Type of Tissue/Character of Wound Bed	X	X	X
PUSH Scores	X	X	X
Health Care Resource Utilization (Wound-Related)		X	X
Safety			
Reason for Early Discontinuation (if applicable)		X	
Adverse Events	X	X	X

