3.2.1. BASELINE VISIT

The following procedures must be performed and recorded at the Baseline (Week 0) visit, gathered from the patient in the clinic unless otherwise specified:

1. Review study procedures and information regarding the study with the subject and obtain written informed consent
2. Review eligibility criteria; inclusion/exclusion (see Section 2.4.2 and Section 2.4.3)
3. For women of childbearing potential, obtain screening urine pregnancy test
4. Obtain demographic information and relevant medical/social history (from chart)
 - a. *Demographics*: age, race (Caucasian, African-American, Hispanic, mixed race, other), gender, marital status, employment status, education (\leq high school, some college, \geq college), insurance status (Medicare, Medicaid, private insurance, other, no insurance) including identification of whether plan is managed care or fee-for-service.
 - b. *Medical/social*
 1. Height (feet/inches), weight (lbs)
 2. Smoking status (current, former, never)
 3. Alcohol (drink every day, a few drinks per week, a few drinks per month, seldom drink, abstain)
 4. Diabetes (yes, no) (from chart)
 5. Injury information (from chart)
 - a) Date of injury
 - b) Injury level (C1-8, T1-12, L1-5)
 - c) American Spinal Cord Injury Impairment Scale (ASIA) score (if known)
 - a. ASIA A – complete, no motor or sensory function is preserved in sacral segments S4-S4
 - b. ASIA B – incomplete, sensory but not motor function is preserved below the neurological level and includes the sacral segments S4-S5.
 - c. ASIA C – incomplete, motor function is preserved below the neurological level, and more than half of key muscles below the neurological level have a muscle grade less than 3.

- d. ASIA D - Incomplete: Motor function is preserved below the neurological level, and at least half of key muscles below the neurological level have a muscle grade of 3 or more.
 - e. ASIA E = Normal: motor and sensory functions are normal.
 - 6. Current antibiotic use
 - 7. Results of any potentially relevant clinical laboratory tests, e.g., albumin, hemoglobin, performed at or within 14 days of baseline.
- 5. Patients will be stratified according to (1) smoking status; and (2) study ulcer Stage. Following stratification, patients will be randomized to study product (Microcyn or sterile saline). Document study pressure ulcer.

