 - a. *Determination of study ulcer*: if a patient has multiple Stage III or Stage IV ulcers, the ulcer with the highest total NPUAP PUSH score will be considered the study ulcer for the duration of the study. This is the ulcer that will be treated with Microcyn or saline. The patient and investigator should be encouraged to treat the patient's other wounds in accordance with the randomization scheme. However, the other wounds may be treated in whatever manner the Investigator deems most appropriate. If the other wounds are treated differently from the study ulcer, the Investigator needs to emphasize the importance of adhering to the study protocol at all times for the study ulcer.
 - b. *Location*: Note anatomical location of study ulcer.
 - c. *Debridement*: (yes/no) If in the opinion of the investigator the ulcer requires debridement, Microcyn or saline solution (as per randomization) is to be used during debridement.
 - d. *Size*: (volume) This is the primary endpoint. The wound size should be measured after debridement if debridement is performed. Size will be determined through clinician measurement with photographic documentation.
 - e. *Description*:

1. % Granulation
 2. % Necrosis
 3. % Eschar
 4. % Slough
 5. Purulence
 6. Odor
 7. Stage
 8. NPUAP PUSH 3.0 total and sub-scores
6. Assess for Adverse Events (AEs) before study product application
 7. Apply study product to wound, while simultaneously demonstrating to patient and/or caregiver how to apply study product to wound (see Section 3.2.3) subject and provide written instruction for use. For patients receiving home care services, home care nursing staff will be provided written instructions on use of product as well as identification of study ulcer, if multiple ulcers are present.
 8. Assess for AEs (post-study product application).
 9. Provide study product to the subject to take home in sufficient quantity to last until next clinic visit.
 10. Review Subject Instructions and Subject Restrictions with patient. Patient will be given these instructions to take home for their and their caregivers' reference and review.

3.2.2. ***FOLLOW-UP VISITS (WEEKS 4, 8, 12, 16, 20, 24)***

The following procedures and information will be performed and recorded at the Week 4, Week 8, Week 12, Week 16, Week 20 and Week 24 visits.

1. Obtain information on current antibiotic use
2. Document study pressure ulcer.

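### No required baseline item records how long the study ulcer has been open, whether it is a recurrence or whether it was closed surgically before, so a chance imbalance in ulcer history cannot be seen or adjusted for

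*Combined protocol and SAP*

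**What the plan says.** The synopsis (Study Visits, Baseline) states that "Initial demographics and a brief medical history will be collected at Baseline from subjects or via chart abstraction after informed consent". The detail is in Section 3.2.1 and in the schedule table, which appears in the synopsis and again as Table 1.

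- **Patient history (3.2.1, item 4):** demographics, height and weight, smoking, alcohol, diabetes, spinal injury details, antibiotics and recent laboratory results. The only onset date is "Date of injury", which is that of the spinal injury.
- **Study ulcer (3.2.1, item 5):** "Note anatomical location of study ulcer", then debridement, size, wound-bed description, Stage and PUSH scores.
- **Schedule tables:** these add bladder management and "Number of Concomitant Ulcers". The latter is a count, not a history of the study ulcer.

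The ulcer criterion for entry is "One or more Stage III or Stage IV pressure wound located anywhere on the body". Neither Section 2.4.2 nor Section 2.4.3 limits ulcer age or excludes recurrences.

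Randomisation is stratified by smoking status and study ulcer Stage (3.2.1, item 5). The primary test is a t-test of percent change in wound size (6.3.1). Regressions on patient characteristics are optional; the synopsis describes them as having "special emphasis on variables that affect healing times, such as diabetes and smoking status".

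**The concern.** The protocol's background suggests that ulcers in this population can be slow to close. It cites a retrospective review of veterans with spinal cord injury in which "over 50% of pressure ulcers did not fully heal over the three-year study period". For the most severe stage, the same review is cited as showing "over 70% of Stage IV ulcers remaining unhealed despite surgeries and multiple hospitalizations". With no limit on ulcer age at entry, a recent ulcer and a long-standing one of the same Stage and size can enter as equivalent subjects.

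If ulcer age carries prognostic information beyond Stage and smoking, two things are lost by not recording it. The variation it explains stays in the error term of the primary comparison, and nobody can check whether the arms happened to differ on it. The second matters most at the interim. That look may include only 20 patients at Week 12, and Section 6.3.1 allows the study to be halted for success on the estimated time to closure.

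**Working it through.** **1. Is the item anywhere in the required data?** I read the synopsis baseline paragraph, both schedule tables and Section 3.2.1, items 4 and 5, for three things: onset date or age of the study ulcer, recurrence, and earlier closure. None appears. The PUSH tool (Appendix B) was not in the copy I read, but the synopsis gives its inputs as surface area, exudate and tissue type, so it would not supply ulcer age.

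**2. Is there a planned figure to reproduce?** No. The synopsis calls the 80 subjects a convenience sample and gives no effect size, standard deviation (SD) or power.

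**3. Inputs for scale.** From the documents: 80 subjects, two-sided 5% level (6.1), an interim of at least 20 subjects (6.1). Assumed, because the documents do not give them: equal allocation (40 per arm; 10 per arm at a 20-patient interim), no dropout, a starting power of 80%, and a share R² of outcome variance explained by ulcer age beyond Stage and smoking of 5%, 10% or 20%.

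**4. Precision.** With 40 per arm, a two-sample t-test has 80% power for a difference of 0.634 SD. Adjustment multiplies the standard error by √(1 − R²), and the equivalent unadjusted sample size is 80/(1 − R²).

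| R² | √(1 − R²) | Cut in standard error | 80/(1 − R²) | Power at 0.634 SD |
|---|---|---|---|---|
| 0.05 | 0.975 | about 3% | 84 | 82% |
| 0.10 | 0.949 | about 5% | 89 | 84% |
| 0.20 | 0.894 | about 11% | 100 | 88% |

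**5. Chance imbalance.** Under simple randomisation the standard error of a standardised baseline difference is √(2/n) with n per arm.

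- 40 per arm: √(2/40) = 0.224. The probability of a gap above 0.25 SD is 26%; above 0.5 SD, 2.5%.
- 10 per arm: √(2/10) = 0.447. The same probabilities are 58% and 26%.

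**6. What a typical imbalance does to the estimate.** A one-standard-error imbalance moves the arm difference by √R² × √(2/n). At 40 per arm this is 0.05, 0.07 or 0.10 SD for the three values of R². At 10 per arm it is 0.10, 0.14 or 0.20 SD. This is the same component as the loss in step 4, viewed within a single trial. It is not a second cost to be added.

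**The case against.** The strongest reply is that nothing here is invalid. Randomisation balances ulcer age in expectation, the unadjusted t-test already carries the resulting variability in its standard error, and its type I error is unaffected. That stands: there is no systematic bias.

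Several stronger readings are tempting, and the documents do not support them.

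- *Ulcer age is a main driver of healing.* No passage links the two. The cited review does suggest a Stage gradient (over 70% unhealed for Stage IV against over 50% overall), and Stage is already a stratification factor.
- *The protocol's figures show ulcers open for years.* They report non-healing over a three-year review window. An ulcer that arose late in the window also counts as unhealed, and no durations or recurrence rates are given.
- *The arms will probably differ in ulcer age.* At 40 per arm a gap above 0.25 SD has about a 26% chance: possible, not likely.
- *The planned regressions will be missing a key predictor.* They are only optional, and their covariates are given as examples.
- *The information will be lost for good.* The chart, the brief medical history or the clinic's usual forms (8.1) may hold an onset date.

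On the last point, part of the concern survives. Nothing requires the item, and retrieving it later in an open-label trial would mean collecting it after allocation, and possibly outcome, are known.

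**Conclusion.** The omission is confirmed in every baseline list, and entry leaves ulcer age unrestricted, so enrolled ulcers may differ widely on it. The consequence is limited to lost precision and an imbalance that cannot be seen. Under the assumed R² of 5% to 20%, 40 per arm and 80% starting power, the gain forgone is about 2 to 8 percentage points of power. It would be smaller if onset dates are imprecise, since measurement error lowers the achievable R².

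The balance check is worth most at the interim, where with an assumed 10 per arm a gap above 0.25 SD is more likely than not (58%) and a decision to halt may follow. A reader might infer that the primary result would be biased or the test unsound; neither follows. This is a low-cost improvement, not a flaw that invalidates the design.

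**What to change.** Add to Section 3.2.1, item 5, ahead of the randomisation step, and to both schedule tables: *Date study ulcer opened (or best estimate in weeks); recurrence at this site (yes/no); earlier surgical closure of this ulcer (yes/no).* Recurrence needs its own item because an ulcer that healed without surgery and reopened would be missed by a question about surgical closure alone.

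In Section 6.3.1, tabulate these items by arm at the interim and final analyses. Pre-specify an adjusted analysis of the primary endpoint with log weeks open as a baseline covariate alongside the stratification factors. Name it among the candidate variables for the optional regressions there and in the synopsis.

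The cost is three short history items at a visit that already takes a history, and one degree of freedom of about 78 for the covariate. Dates for old ulcers will be approximate. No treatment, visit or eligibility rule changes.

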1. INTRODUCTION AND BACKGROUND

A pressure ulcer (also called a wound or sore) is a localized injury to the skin and/or underlying tissue usually over a bony prominence, as a result of pressure, or pressure in combination with shear and/or friction. Pressure ulcers are staged into Stage I, II, III, IV and unstageable. The National Pressure Ulcer Advisory Panel (NPUAP) has published guidelines on the staging of ulcers for clinicians and patients to more consistently describe wounds. The full guidelines for staging are listed in Appendix A. The focus of the present study is Stage III and Stage IV ulcers, which are described in the NPUAP guidelines as:¹

- A stage III ulcer exhibits full thickness tissue loss. Subcutaneous fat may be visible but bone, tendon or muscle are not exposed. Slough may be present, but does not obscure the depth of tissue loss. May include undermining and tunneling.
- A Stage IV ulcer exhibits full thickness tissue loss with exposed bone, tendon or muscle. Slough or eschar may be present on some parts of the wound bed. Often include undermining and tunneling.

Several published guidelines on the treatment (and prevention) of pressure ulcers are available through the Agency for Healthcare Research and Quality (AHRQ) guideline repository.² Included in this repository are the 2010 Association for the Advancement of Wound Care, guidelines, which give the following recommendations for treatment:³

1. Remove/alleviate all causes of pressure ulcer damage
2. Debride, cleanse, and dress the wound
3. Implement advanced or adjuvant interventions if insufficient response seen
4. Surgical interventions if continued insufficient response
5. Documentation of response

[figure not shown]
¹ NPUAP, 2007, available at <http://www.npuap.org/>.

² www.guidelines.gov

³ Association for the Advancement of Wound Care (AAWC). Association for the Advancement of Wound Care Guideline of Pressure Ulcer Guidelines. Malvern (PA): Association for the Advancement of Wound Care (AAWC); 2010. 14 p

6. Palliative care if applicable

While dated, the 1994 Agency for Healthcare Policy Research (AHCPR, now known as AHRQ) guidelines present a heuristic for assessment and treatment of pressure ulcers that still holds today (Figure 1).

The numbers above represent “nodes” of care with nodes 1-4 representing the four basic components of an effective pressure ulcer care plan: (Node 1) necrotic tissue debridement; (Node 2) initial wound cleansing and repeated cleansing with each dressing change; (Node 3), prevention, diagnose and treatment of infection; and (Node 4), using a wet ulcer dressing that keeps surrounding tissue dry. Nodes 5-14 as shown above represent

assessment and reassessment of the healing strategy and its outcome(s) to ensure optimal healing.

Spinal cord injured patients are an especially vulnerable population for pressure ulcers because of both the immobility rendered by resultant paralysis and of impaired sensation. The National Spinal Cord Injury Statistical Center (NSCISC) estimates that between 231,000 and 311,000 Americans are living with a spinal cord injury (SCI), with approximately 12,000 new cases each year.⁴ As a result of increased research and interest, remarkable progress has been made in improving the quality of life and life expectancy for SCI patients. Secondary complications, however, continue to challenge individuals living with SCI and their caregivers. Pressure ulcers, in particular, “remain the single most important medical complication in terms of loss of time in educational or vocational pursuits, increased hospital stay and resulting financial expenditures.”⁵ In patients with paraplegia, pressure ulcers are the leading cause of rehospitalization;⁶ across injury levels, sepsis from pressure ulcers and genitourinary tract infections are the leading cause of death in Veterans with SCI.⁷

Recent cost estimates on treating pressure ulcers in SCI patients indicate a range of \$2,000 to \$70,000 per wound, with an annual aggregate cost of approximately \$2.2 to \$3.6 billion in the United States alone.⁸ In a retrospective study reviewing medical records of veterans with spinal cord injury, it was found that over 50% of pressure ulcers did not fully heal over the three-year study period, with over 70% of Stage IV ulcers remaining unhealed despite surgeries and multiple hospitalizations.⁹

⁴ *Spinal Cord Injury Facts and Figures at a Glance*, National Spinal Cord Injury Statistical Center, Birmingham, Alabama, February 2010, <https://www.nscisc.uab.edu>.

⁵ Jackson, AB., *Secondary Conditions of Spinal Cord Injury*, Spinal Cord Injury Network, <http://www.spinalcord.uab.edu/show.asp?durki=32106>.

